### 2.6.5 Sensitivity analyses

CCI

## 2.6.6 Supplementary analyses

No supplementary analysis will be performed for secondary endpoints.

## 2.7 Safety analyses

For all safety analyses, the Safety set will be used. Safety summaries include data from the on-treatment period with the exception of baseline data which will be summarized where appropriate (e.g., change from baseline summaries). In particular, summary tables for AEs will summarize treatment-emergent AEs (i.e. with a start date on or after the first treatment).

### 2.7.1 Adverse events (AEs)

The number and percent of patients with treatment emergent AEs (events started after the start of study treatment or events present prior to start of study treatment but increased in severity based on PT) will be summarized in the following ways:

- by primary SOC and PT
- by primary SOC, PT, and maximum severity

Separate summaries will be provided for study treatment related AEs, SAEs, AEs leading to discontinuation, and AEs leading to dose interruption for Coartem in Parts B & C.

A patient with multiple AEs within a primary SOC is only counted once towards the total of the primary SOC.

#### 2.7.1.1 EudraCT and clinicaltrials.gov requirements

For legal requirements of clinicaltrials.gov and EudraCT, two on-treatment tables are required:

- On-treatment deaths resulting from SAEs suspected to be study drug related and SAEs regardless of study drug relationship by SOC and PT
- Non-serious AEs regardless of study drug relationship, with an incidence rate greater than 5% by SOC and PT

These summaries will include any events starting or worsening in the on-treatment period.

If for the same patient, if several consecutive AEs (irrespective of study treatment causality, seriousness, and severity) occurred with the same SOC and PT:

- a single occurrence will be counted if there is  $\leq 1$  day gap between the end date of the preceding AE and the start date of the consecutive AE
- more than one occurrence will be counted if there is  $> 1$  day gap between the end date of the preceding AE and the start date of the consecutive AE

The presence of at least one SAE / SAE suspected to be study drug related / non SAE has to be checked in a block e.g., among AEs in a  $\leq 1$  day gap block, if at least one SAE is occurring, then one occurrence is calculated for that SAE.

### **2.7.1.2 AEs of special interest / grouping of AEs**

The number and percent of patients with treatment emergent signs and symptoms of severe malaria (i.e., those categorized as Severe Malaria on the AE eCRF) will be summarized by SOC and PT.

AEs of special interest are defined in the Case Retrieval Sheet (CRS) which is updated for each MEDDRA dictionary. The CRS data are stored in TMS.ECRS SAS dataset corresponding to a subset of eCRS SAS view for which the following filtering criteria are applied:

- Drug code = KAE609 (Cohorts B1, B2, & C2), KAF156 (Cohorts B2 & C2)
- Latest version of MedDRA at the time of final database lock
- End date is null (this means this is the latest CRS version)

The number and percent of patients with these special AEs will be summarized. In addition, listings of related AEs will be provided.

Liver related events and QTcF abnormalities will be summarized (see [Sections 2.7.3](#) and [Section 2.7.4.1](#))

### **2.7.2 Deaths**

All deaths will be listed.

### **2.7.3 Laboratory data**

Descriptive statistics will be generated for all clinical laboratory tests performed (actual values and changes from baseline) for three groups of laboratory tests (hematology, clinical chemistry and urinalysis).

Shift tables using the low/normal/high classification will be used to compare baseline to the worst post-baseline value.

Summary with frequency and percent of patients with liver related events (based on AST, ALT, and Total Bilirubin) using the Novartis standard table will be provided.

Boxplots for hematology and biochemistry parameters will be provided.

Listing for patients with lab values outside the normal range (per normal ranges in the source dataset) will be provided. If there is any abnormal lab value for a patient, all measurements of this lab value for the patient will be presented with the abnormal values flagged.

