5.2 Exclusion criteria

Part A:

Patients meeting any of the following criteria are not eligible for inclusion in this part of the study.

1. Patients with signs and symptoms of severe/complicated malaria at screening
2. Mixed *Plasmodium* infection (i.e., infection with more than one malaria species) at screening
3. Use of any anti-malarial treatment or antibiotics with anti-malarial activity (or prohibited medication) in the preceding 14 days or at least 5 half-lives whichever is longer before screening
4. Moderate to severe anemia, chronic hemoglobinopathy (Hemoglobin level < 8 g/dL), or known chronic underlying disease such as sickle cell disease at screening
5. Active infections including tuberculosis, or history of taking anti-tuberculosis medications within 12 months prior to screening
6. History of, or current alcohol use disorder defined as five or more drinks on the same occasion on each of 5 or more days in the past 30 days prior to screening
7. Known clinically significant liver disease (e.g., chronic hepatitis, liver cirrhosis (compensated or decompensated), history of hepatitis B or C, hepatitis A or B vaccination in the last 3 months, known gallbladder or bile duct disease, acute or chronic pancreatitis.

Clinical or laboratory evidence of any of the following at screening:

- AST/ALT > 3 x the upper limit of normal range (ULN), regardless of the level of total bilirubin
 - AST/ALT > 1.5 and ≤ 2 x ULN and total bilirubin is $> \text{ULN}$
 - Total bilirubin > 2 x ULN, regardless of the level of AST/ALT
8. Any known/suspected immunosuppressive or immunodeficient condition, including human immunodeficiency virus (HIV) infection at screening
 9. Known disturbances of uncorrected electrolyte balance, e.g., hypokalemia, hypocalcemia or hypomagnesemia
 10. Severe malnutrition (Body Mass Index (BMI) < 16.0) at screening
 11. Severe vomiting, defined as more than 3 times in the 24 hours prior to screening or severe diarrhea defined as watery stools more than 3 times in the 24 hours prior to screening
 12. Pregnant or nursing (lactating) women

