19. History of malignancy of any organ system (other than localized basal cell carcinoma of the skin or *in situ* cervical cancer), treated or untreated, within the past 5 years of screening, regardless of whether there is evidence of local recurrence or metastases
20. Patients with serum creatinine $\geq 2 \times$ ULN in the absence of dehydration at screening. In case of dehydration, patients with serum creatinine $\geq 2 \times$ ULN after oral or parenteral rehydration
21. Patients taking drugs that are strong inducers of CYP3A4 such as rifampicin, carbamazepine, phenytoin, St. John's wort (*Hypericum perforatum*) at screening
22. History of hypersensitivity to any of the study treatments or its excipients or to drugs of similar chemical classes
23. Use of herbal medication within one week of screening

24. Use of other investigational drugs within 5 half-lives of screening, or within 30 days or until the expected pharmacodynamic (PD) effect has returned to baseline, whichever is longer; **or longer if required by regulations.**
25. Previous participation in any malaria vaccine study or received malaria vaccine in any other circumstance
26. Previous participation in the same cohort within this study

Part B:

Patients meeting any of the following criteria are not eligible for inclusion in this part of the study.

The same exclusion criteria from Part A apply in Part B with the addition of the following:

1. Women of child-bearing potential, defined as all women physiologically capable of becoming pregnant, unless they are using methods of contraception defined in the cohort-specific sections ([Section 12](#)). Additionally, for combination therapy in Part B, the more conservative contraception requirement will be used.

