8.4.6 Other safety evaluations

Signs and symptoms of severe malaria

Danger signs:

- not able to drink
- vomiting > twice within preceding 24 hours
- one convulsion within preceding 24 hours
- unconscious state
- unable to sit or stand

Signs of severe malaria:

Severe *P. falciparum* malaria is defined as one or more of the following, occurring in the absence of an identified alternative cause and in the presence of *P. falciparum* asexual parasitemia:

- Impaired consciousness (Glasgow coma score < 11 in adults)
- Prostration (generalized weakness i.e., unable to sit, stand or walk without assistance)
- Multiple convulsions (more than two episodes within 24 hours)
- Acidosis (a base deficit of > 8 mEq/L or if not available a plasma bicarbonate level of < 15 mmol/L or venous plasma lactate \geq 5 mmol/L. Severe acidosis manifests clinically as respiratory distress i.e., rapid, deep, labored breathing)
- Hypoglycemia (blood or plasma glucose < 2.2 mmol/L; < 40 mg/dL)
- Severe malarial anemia (hemoglobin concentration \leq 5 g/dL or a hematocrit of \leq 15% in children < 12 years of age (< 7 g/dL and < 20% respectively in adults) with a parasite count > 10,000/ μ L)
- Renal impairment (plasma or serum creatinine > 265 μ mol/L (3 mg/dL) or blood urea > 20 mmol/L)
- Jaundice (plasma or serum bilirubin > 50 μ mol/L (3 mg/dL) with a parasite count > 100,000/ μ L)
- Pulmonary edema (radiologically confirmed or oxygen saturation < 92% on room air with a respiration rate > 30/min, often with chest indrawing and crepitation on auscultation)
- Significant bleeding (including recurrent or prolonged bleeding from the nose, gums of venipuncture sites, hematemesis or melena)
- Shock (compensated shock i.e., capillary refill \geq 3s or temperature gradient on leg but no hypotension; decompensated shock i.e., systolic blood pressure < 70 mm Hg in children or < 80 mm Hg in adults with evidence of impaired perfusion)
- Hyperparasitemia (*P. falciparum* parasitemia > 10%)

If a patient experiences and danger signs / signs of severe malaria, the investigator should report the event as an SAE following the guidance provided in [Section 8.6.3](#). Local guidance should be followed for the treatment of these danger signs / signs of severe malaria.

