Categorical Analysis of QT/QTc interval data based on the number of patients meeting or exceeding predefined limits in terms of absolute QT/QTc intervals or changes from baseline will be presented. In addition, a listing of these patients will be produced (by each single anti-malarial agent, study part and treatment group).

All ECG data will be listed by each single anti-malarial agent, study part, treatment group, patient and visit/time, abnormalities will be flagged. Summary statistics will be provided by each single anti-malarial agent, study part, treatment group, and visit/time.

Clinical laboratory evaluations

All laboratory data will be listed by each single anti-malarial agent, study part, treatment group, patient, and visit/time and if normal ranges are available abnormalities will be flagged. Summary statistics will be provided by each single anti-malarial agent, study part, treatment group, and visit/time. Shift tables for each single anti-malarial agent and study part using the low/normal/high classification will be used to compare baseline to the worst post-treatment value.

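### Low/normal/high shift tables hide further worsening from an abnormal baseline, and no visible non-liver laboratory table counts the patients concerned

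*SAP*

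**What the plan says.** SAP 2.7.3 plans five laboratory outputs:

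- descriptive statistics of values and of changes from baseline;
- shift tables;
- a count of patients with liver-related events, built on AST, ALT and total bilirubin;
- boxplots for haematology and biochemistry;
- a listing that shows every measurement of a test for a patient with any abnormal value of it.

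The shift rule is "Shift tables using the low/normal/high classification will be used to compare baseline to the worst post-baseline value". Protocol 9.4.2 agrees, with tables "using the low/normal/high classification will be used to compare baseline to the worst post-treatment value". Neither section names a grade, a notable limit or a size of change for any non-liver test.

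Protocol 5.2 allows some abnormal values at entry. Criterion 4 begins "Moderate to severe anemia, chronic hemoglobinopathy (Hemoglobin level < 8 g/dL" and goes on to chronic conditions such as sickle cell disease. Criterion 20 excludes "Patients with serum creatinine $\geq 2 \times$ ULN in the absence of dehydration at screening", with the same limit after rehydration in dehydrated patients.

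Laboratory worsening can also surface elsewhere. Protocol 8.4.6 lists signs of severe malaria, to be reported as SAEs. SAP 2.7.1.2 counts patients with such events, meaning "those categorized as Severe Malaria on the AE eCRF". Under Protocol 8.6.1 an abnormal value becomes an AE if it causes signs or symptoms, is judged clinically significant or needs therapy. SAP 2.7.1 counts patients with AEs by preferred term.

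**The concern.** A shift table is the usual place to read how many patients in each arm got worse on a laboratory test. Here it can show only patients who cross a limit of normal. Acute malaria patients may enter with low haemoglobin or raised creatinine. For them the table cannot separate no change from marked further worsening.

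Laboratory results are part of the secondary safety objective, which compares the combination with the standard of care in Part B (and in Part C under the SAP). For non-liver tests, the number who worsened from an abnormal start would have to be read from listings or from investigator-judged AEs. It would not come from a count fixed in advance.

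**Working it through.** The plan gives no figure to reproduce. The check asks which cell a patient falls in, and which other planned output would count that patient.

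**Cell logic.** Let L and U be the limits of normal, b the baseline and w the worst value.
- If b < L and w ≤ b, both are low, so the cell is low-to-low whatever the size of b − w.
- If b > U and w ≥ b, both are high, so the cell is high-to-high whatever the size of w − b.

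**Haemoglobin.** The documents give no lower limit of normal; 11 to 13 g/dL is assumed. A baseline just under the limit is mildly low and enrollable on any reading of criterion 4. A fall from there to 8 g/dL stays low-to-low:

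| Assumed limit (g/dL) | Fall to 8 (g/dL, just under) | Relative fall |
|---|---|---|
| 11 | 11 − 8 = 3 | 3/11 = 27% |
| 12 | 12 − 8 = 4 | 4/12 = 33% |
| 13 | 13 − 8 = 5 | 5/13 = 38% |

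If criterion 4 is read as a single floor at 8 g/dL, a patient could enter at 8.0 and fall to 6.9. That is 8.0 − 6.9 = 1.1 g/dL, or 1.1/8.0 = 13.75%, again with no change of cell.

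**Creatinine.** Entry is allowed between 1 and 2 × ULN. A rise from 1.9 to 1.9 × 2 = 3.8 × ULN is high-to-high.

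**Severe-malaria route.** All signs must be "occurring in the absence of an identified alternative cause and in the presence of" *P. falciparum* asexual parasites.
- The adult anaemia sign is "< 7 g/dL and < 20% respectively in adults) with a parasite count" above 10,000/µL. The falls to 8 g/dL in the table do not reach it.
- The renal sign is creatinine above 265 µmol/L ("3 mg/dL) or blood urea > 20 mmol/L"). The 3.8 × ULN case passes 3 mg/dL when ULN exceeds 3/3.8 = 0.79 mg/dL, so this route can catch it during parasitaemia.
- A doubling does not pass 3 mg/dL if the baseline is at most 3/2 = 1.5 mg/dL. At an assumed ULN of 1.0, 1.2 or 1.4 mg/dL that is 1.50, 1.25 or 1.07 × ULN, all inside the entry limit. The urea figure could still apply.
- The 1.5 mg/dL bound matters only while this route is open. After clearance, or when another cause such as study drug is identified, the route is closed for a doubling from any raised baseline.

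**Other outputs in SAP 2.7.3.** Descriptive statistics and boxplots show distributions. The listing shows individuals. The liver table counts patients, but only for AST, ALT and bilirubin.

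**Comparison within the SAP.** Section 2.7.4.1 counts patients with QTcF increases of more than 30 to 60 ms and of more than 60 ms, besides absolute bands. Table 2-4 combines level and change for adult blood pressure and pulse, for example systolic pressure of at least 180 mmHg with a rise of at least 20 mmHg. Visible haematology and renal outputs have no counterpart.

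**The case against.** Four points can be made for the plan.

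1. *A count may exist out of sight.* The SAP abbreviation list has CTC and CTCAE. The protocol list has CTC, drug-induced nephrotoxicity, eGFR and serum creatinine. None has a visible use. The table shells are a separate document, and protocol Table 8-2, the second appendix and SAP section 4 are redacted. This stands. A reader might infer that the plan contains no such count at all; the documents support only that none is visible.

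2. *The AE route is broad.* Protocol 8.4.4 has every abnormal result assessed against the AE criteria. Protocol 8.6.1 directs attention to clinically notable ranges and to significant changes from baseline. A reported case would be counted by arm. This stands in part. Much of the route rests on investigator judgement with treatment open (Protocol 6.3.2), and severity is graded by effect on activities, not by the laboratory value.

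3. *Listings suffice in small arms.* The SAP shows 30:30 and 80:40. A count could indeed be taken from the listing, but its limits would then be chosen after the data were seen. Normal ranges from each local laboratory are a defensible default for the existing table; the request is for an addition.

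4. *The 8 g/dL floor is one reading.* Criterion 4 may exclude moderate anaemia separately, with 8 g/dL attached only to haemoglobinopathy. This stands, which is why the haemoglobin table starts from mildly low values.

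A reader might also infer that safety data are lost or that patients are less well protected. The documents do not support that: changes from baseline, boxplots, full listings, AE tables and SAE reporting all remain.

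**Conclusion.** The point holds as a minor gap in how a secondary safety comparison is reported. The three-class rule cannot show same-direction worsening from an abnormal baseline, and no visible non-liver laboratory table counts those patients. The AE and severe-malaria routes are real but partial.

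No patient number is claimed. The limits of normal used above are assumptions, and the cell logic does not depend on them. The eligibility limits come from the June 2023 protocol amendment, while the SAP follows protocol version 03 of 20 March 2024, so they should be rechecked there, including for Part C. Confidence is medium, because the shells and redacted text could already meet the point.

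**What to change.** In SAP 2.7.3, for haemoglobin, platelets, neutrophils and creatinine as far as collected:

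- add a shift from baseline CTCAE grade to worst post-baseline CTCAE grade, with low and high directions separate, and name the CTCAE version;
- count patients by creatinine multiple of baseline, with cut-points fixed in the SAP (a doubling, for example). A grade shift still hides change inside one grade, and this count covers that for creatinine.

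If the shells or redacted text already hold such counts, cite them in 2.7.3 instead.

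The cost is a paragraph of SAP text, a few extra tables from data already collected, and harmonisation of units across local laboratories. It also brings in a grading scale that no visible analysis now uses, although the SAP already lists its abbreviation.

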### **2.7.4 Other safety data**

#### **2.7.4.1 ECG and cardiac imaging data**

PR, QRS, QT, QTcF, and RR intervals will be obtained from 12-lead ECGs. ECG data will be read and interpreted (local and centrally). Local readings will be used only for site decision making purposes and not for any analyses; only central readings will be used for the summaries and listings described below.

When ECG triplicates are collected at any assessment, the average of the ECG parameters at that assessment will be used in the analyses.

Categorical analysis of QT/QTc interval data based on the number of patients meeting or exceeding predefined limits in terms of absolute QT/QTc intervals or changes from baseline will be presented.

The number and percent of patients with notable ECG values will be presented.

- QT, QTcF
  - New value of  $> 450$  and  $\leq 480$  ms
  - New value of  $> 480$  and  $\leq 500$  ms
  - New value of  $> 500$  ms
  - Increase from baseline of  $> 30$  ms to  $\leq 60$  ms
  - Increase from baseline of  $> 60$  ms
- HR (= 60/RR (sec)) for age  $\geq 18$  years
  - Increase from baseline  $>25\%$  and to a value  $> 100$  bpm
  - Decrease from baseline  $>25\%$  and to a value  $< 50$  bpm
- HR (= 60/RR (sec)) for age  $< 18$  years
  - $> 90$ th percentile defined in [Table 2-2](#)
  - $< 10$ th percentile defined in [Table 2-2](#)
- PR
  - Increase from baseline  $>25\%$  and to a value  $> 200$  ms
  - New value of  $> 200$  ms
- QRS
  - Increase from baseline  $>25\%$  and to a value  $> 120$  ms
  - New values of QRS  $> 120$  ms

ECG data will be summarized by presenting summary statistics of observed data and change from baseline by time point.

A listing will be provided for patients with any notable values defined above. If there is any notable value of an ECG for a patient, all measurements of this ECG value for the patient will be presented in this listing with the notable values flagged. A summary and listing will also be provided of ECG findings for which there is a clinically significant ECG abnormality.

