**Table 2-2 Heart rate cut-offs (bpm) for 2 to  $<18$  years based on centile charts**

Age Range	10 th percentile	90 th percentile
2 - $<3$	92	128
3 - $<4$	86	123
4 - $<6$	81	117
6 - $<8$	74	111
8 - $<12$	67	103
12 - $<15$	62	96

Age Range	10 th percentile	90 th percentile
15 – <18	58	92

Reference: Lancet. 2011 March 19; 377(9770): 1011–1018. doi:10.1016/S0140-6736(10)62226-X.

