### 2.7.4.2 Vital signs

Summary statistics will be provided by visit/time.

The number and percent of patients with newly occurring notable vital signs will be presented; for Part B they will be separated by <18 years ([Table 2-3](#)) and ≥18 years ([Table 2-4](#)).

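### SAP 2.7.4.1: the under-18 heart-rate criterion is the only notable-ECG criterion without a baseline condition, which dilutes the paediatric heart-rate table and conflicts with the pulse rule in 2.7.4.2

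*SAP*

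**What the plan says.** SAP 2.7.4.1 (ECG and cardiac imaging data) introduces its criteria with "The number and percent of patients with notable ECG values will be presented", so the unit is the patient. The criteria are:

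- QT and QTcF: a new value in a given band, or an increase from baseline.
- PR and QRS: a new value above a limit, or an increase of more than 25% to above that limit.
- Heart rate, age 18 and over: a change from baseline of more than 25%, ending above 100 or below 50 bpm.
- Heart rate, age under 18: above the 90th percentile of Table 2-2 (one bullet) or below the 10th (a second bullet). Neither bullet mentions baseline or a new value.

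The Table 2-2 title says that its limits are for 2 to under 18 "years based on centile charts". For triplicates, "the average of the ECG parameters at that assessment will be used in the analyses".

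For vital signs, SAP 2.7.4.2 says: "The number and percent of patients with newly occurring notable vital signs will be presented". The paediatric pulse limits in Table 2-3 are the same numbers as in Table 2-2.

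Section 2.7.4.1 also plans observed values and changes from baseline by time point, a listing of patients with any notable value, and a summary and listing of clinically significant ECG abnormalities.

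**The concern.** The same child's heart rate is judged by two rules in adjacent sections: as an ECG value it counts whenever it is outside the centiles, and as a pulse it counts only if the abnormality is new. Nothing in the visible text explains the difference, and the ECG criteria list is not interrupted by a redaction. It reads as an omission.

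The limits are the 10th and 90th centiles of a reference population, so a sizeable share of normal children will be called notable. A child outside a limit before dosing who stays there is counted as if the abnormality had started on treatment. The table therefore mixes normal variation, entry status and drug effect. It covers all of Part C (120 evaluable children planned in Cohort C2) and the adolescents in Part B.

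**Working it through.** The plan states no expected flag rate, so there is no figure to reproduce.

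**Inputs from the SAP.** Table 2-2 limits (for example 74 and 111 bpm at 6 to under 8 years; 58 and 92 at 15 to under 18), and the C2 sizes of 80 on combination and 40 on Coartem.

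**Assumptions.** The number of post-dose ECG time points is not visible, because the assessment schedule is redacted, and no within-patient correlation is given. I use 1 to 5 readings and correlations of 0.5 to 0.9. Children are taken to follow the reference distribution, and each row is fitted with a normal curve: mean = (P10 + P90)/2 and SD = (P90 − P10)/(2 × 1.2816). For 6 to under 8 years the mean is (74 + 111)/2 = 92.5 and the SD is 37/2.563 = 14.4 bpm.

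**Step 1, per reading.** 10% below P10 + 10% above P90 = 20%. With whole-bpm values and strict inequalities, the fitted rows give 18.7–18.8%. So the figure is about one in five.

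**Step 2, per patient.** For k independent readings the chance of at least one flag is 1 − 0.8^k: 49% for k = 3 and 67% for k = 5. Heart rates within a child are correlated, so I simulated equicorrelated normal readings plus a baseline (200,000 or more patients per setting). Three rules were compared: as written; newly occurring (baseline not already beyond the same limit); and outside the limit with a change of more than 25% from baseline in the same direction. The last column gives the range over the seven Table 2-2 rows.

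| Correlation | Readings | As written | Newly occurring | >25% change |
|---|---|---|---|---|
| 0.5 | 1 | 20% | 13.5% | 2–6% |
| 0.5 | 3 | 43% | 31% | 6–15% |
| 0.5 | 5 | 57% | 43% | 10–22% |
| 0.7 | 1 | 20% | 10.7% | 0.5–2.4% |
| 0.7 | 3 | 38% | 23% | 1.5–6.5% |
| 0.7 | 5 | 48% | 32% | 2–10% |
| 0.9 | 1 | 20% | 6% | <1% |
| 0.9 | 3 | 30% | 13% | <1% |
| 0.9 | 5 | 35% | 16% | <1% |

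These rates combine the high and low flags. For one direction alone, three readings as written give 15% (correlation 0.9) to 22% (0.5).

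**Step 3, in C2 numbers.** With three readings, 30–43% of 80 is about 24–34 children on the combination, and 30–43% of 40 is about 12–17 on Coartem, flagged with no drug effect.

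**Step 4, how much signal is lost.** No test is planned on this table, so power serves only as a gauge. Take a 10 bpm rise on the combination, one reading, the 6 to under 8 row, 40 versus 80, two-sided 5%:

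- Either flag: 20% to 30%, power about 21%.
- High flag alone: 10% to 28%, power about 62%.
- Mean change from baseline at correlation 0.5: SD of change = 14.4 × √(2 × 0.5) = 14.4; standard error = 14.4 × √(1/40 + 1/80) = 2.79; 10/2.79 = 3.58; power about 95%.

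The categorical table is weaker, but the planned change-from-baseline summary would show the shift.

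**The case against.** A reader might infer that real drug effects would be buried. The documents do not support that. High and low flags are separate bullets. Section 2.7.4.1 also reports change from baseline by time point and clinically significant abnormalities, and 2.7.4.2 reports newly occurring pulse abnormalities at the same cut-offs. Parts B and C have a randomized Coartem arm that shows the background rate. The QT, PR and QRS criteria are unaffected. All of this stands: the loss is dilution in one table.

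A reader might also infer that at least one in five normal readings must be flagged. The whole-bpm calculation gives slightly less. These patients also have acute malaria and are not a reference sample. If fever raises heart rate at entry, high flags would exceed 10% and low flags would fall below it; the documents give no figure. Low flags already present at entry may also be rare in older adolescents. Protocol 5.2 excludes a resting heart rate below 60 bpm, and that criterion carries to Part B, while the lower limit at 15 to under 18 is 58. Part C entry criteria cannot be checked, because the supplied protocol predates Part C.

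Nor is it a defect in itself that adults and adolescents have different rules. The pulse criteria also differ by age, and the safety comparison is between arms. What remains is the missing baseline condition and the mismatch with 2.7.4.2.

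**Conclusion.** The point holds as a minor inconsistency with a measurable effect. The under-18 heart-rate criterion is the only one in its list without a baseline condition, and it departs from the pulse rule at identical cut-offs. About 20% of reference-normal children would be flagged at one reading and about 30–43% at three, and abnormalities present at entry are counted as if new.

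The one-reading figure follows from the centiles. The multi-reading figures rest on the assumed number of readings, correlations of 0.5 to 0.9, normality, and the reference distribution holding in this population. The issue is confined to one descriptive safety table and the listing that depends on it. It does not touch the primary analysis.

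**What to change.** In SAP 2.7.4.1, for age under 18, count a heart rate as notable if it is above the upper Table 2-2 limit and more than 25% above baseline, or below the lower limit and more than 25% below baseline. This mirrors the adult rule. State how a child without a baseline ECG is handled.

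Do not also require a baseline within the limits. That would be stricter than the adult rule and would miss a child who enters outside a limit and worsens. For example, a 7-year-old going from 115 (upper limit 111) to 150 rises by 35/115 = 30% and should count, as an adult with those values would.

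At minimum, restrict the count to newly occurring values, as 2.7.4.2 does. That aligns the two sections but leaves more background (32% rather than 2–10% at correlation 0.7 with five readings).

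Keep the patient listing on the Table 2-2 limits alone. It is now defined through the notable criteria, so narrowing them without this step would drop patients from it.

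The cost is a line or two of SAP text and a small programming change. The downside is fewer flagged values in the summary: a child at 92.5 bpm would need to exceed 92.5 × 1.25 = 115.6 rather than 111.
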